Additional sensitivity analysis using tipping point approach with multiple imputation will be performed to assess the robustness of the results due to data that may be missing not-at-random (MNAR). Multiple imputation will be based on monotone missing data structure of the change from baseline score using regression option in PROC MI. Monotone missing data structure will be achieved using MCMC option of PROC MI. After each imputation, a fasinumab patient's imputed data will subtract k (e.g., 20%, 40%, 100%, ...) times the treatment effect at each corresponding time point. By progressively increasing coefficient k, the sensitivity analysis will explore the tipping point, ie, the upper bound on the critical value of coefficient k at which conclusion from the primary analysis will be overturned ( $p > 0.05$ ). Additional sensitivity analyses will be performed the same way for the primary and selected secondary endpoints using the PPS.

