- Step 3: The initially missing and now imputed data for patients discontinued from the study treatment due to lack of efficacy or AEs will be adjusted to be centered at the mean baseline value for that treatment group, i.e., final imputed score = imputed score under MAR - (mean change from baseline score at the post-baseline time point for the treatment group based on patients on treatment with non-missing data at that time point).

Each imputed data set will be analyzed using the MMRM with terms for baseline score corresponding to the primary efficacy variable (e.g. WOMAC pain subscale score at baseline for the analysis of change from baseline in WOMAC pain subscale score), treatment, randomization strata, visit, and treatment by visit interaction. The MMRM will be performed using the MIXED procedure in the Statistical Analysis System (SAS) with an unstructured covariance matrix to model the within-patient errors. Denominator degrees of freedom will be estimated using Kenward-Roger's approximation.

- The results from the 50 analyses will be combined using Rubin's formulae (PROC MIANALYZE). The least squares mean estimates for the mean change from baseline to week 16, as well as the difference of the estimates between fasinumab and placebo, with the corresponding standard error, p-value and associated 95% confidence interval will be provided.

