5.2.7.1.2. Sensitivity Analyses

Sensitivity analyses will be performed to assess the robustness of the results generated for the primary efficacy variables.

Analysis of Treatment Policy Estimand

Sensitivity analysis of treatment policy estimand for the co-primary endpoints will be performed using similar analysis method as the primary efficacy analysis. The treatment policy estimand is the difference in means between each fasinumab dose+protocol-defined rescue medication and placebo+protocol-defined rescue medication in the change from baseline to week 16 in the WOMAC pain and physical function scores in the FAS-substudy, regardless of study treatment discontinuation prior to week 16 and regardless of whether or not prohibited medication had been taken. Hence, data from all patients, including data collected after discontinuing treatment up to week 16 will be used in this sensitivity analyses. Missing data for patients discontinued from the study up to week 16 will be imputed assuming the WOMAC scores would on average return to baseline values using the same approach as in Section 5.2.7.1.1.

Tipping Point Analysis

Sensitivity analysis using a tipping point approach with multiple imputation will be performed to assess the robustness of the results due to data that may be missing not-at-random (MNAR).

This approach will introduce a sensitivity parameter, δ , corresponding to a percentage (e.g., 20%, 40%, ..., 100%, 200%, ...) of the treatment effect at each corresponding visit. Estimations will be performed using multiple imputation methodology. Missing data up to week 16 time-point will be imputed 50 times to generate 50 complete datasets by using SAS procedure PROC MI for each δ following the 2 steps below:

- Step 1: The monotone missing pattern is induced by Markov Chain Monte Carlo (MCMC) method in MI procedure using seed number [REDACTED].

- Step 2: The missing data at subsequent visits will be imputed using the regression method for the monotone pattern with seed number [REDACTED] and adjustment for covariates including treatment groups, randomization strata, relevant baseline and values from preceding visits. For missing data due to adverse events or lack of efficacy, δ will be added to the imputed values ($\delta = 0$ corresponds to the MAR assumption).

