Each imputed data set will be analyzed using the MMRM model with treatment, randomization strata, and relevant baseline included in the model. For each δ the SAS MIANALYZE procedure will be used to generate valid statistical inferences by combining results from the 50 analyses using Rubin's formula. By progressively increasing δ , the sensitivity analysis will explore the tipping points, e.g., δ value when the p-value for a treatment comparison is above 0.0167, 0.0333 or 0.05. Results will be then summarized using summary tables and graphs.

Per Protocol Set Analysis

Sensitivity analyses based on the PPS will be performed using the MMRM approach.

Subgroup Analysis

Descriptive analyses will be performed on the primary endpoints and key secondary endpoint of PGA to summarize the treatment effects across subpopulations defined by baseline randomization strata (index joint and K-L score category), demographics (age group, sex, race) and baseline characteristics (weight and BMI categories). Subgroup analysis based on other medical conditions may also be performed. Forest plots for the subgroup analysis will be provided.

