5.2.7.3. Analysis of Additional Secondary Efficacy Variable(s)

Analyses of continuous variables in other secondary endpoints will use the same analysis method as the primary efficacy variables.

No control for multiplicity will be made for these analyses. Tests for comparing each fasinumab dose versus placebo will utilize a nominal 2-sided alpha level of 0.05.

NRS

For the analysis of average weekly walking index joint pain using the NRS pain scale, baseline is defined as the average of the non-missing values during 7 days prior to taking study drug. For each week, the average of the non-missing values during the 7 days on or prior to that week will be used. If all values are missing for the 7 days, the value for that week is set to missing.

The MMRM model will be used for the analysis with terms for the randomization strata (K-L category [2-3 vs. 4] and index joint [hip or knee], geographic region), treatment, week treatment-by-week interaction as fixed effects, and baseline NRS value as a covariate. The least-squares (LS) means for the mean change from baseline to each week as well as the LS mean differences between fasinumab doses and placebo, with their corresponding standard errors (SEs), p-values and associated 95% confidence intervals, will be provided from the MMRM. If the model does not converge using unstructured covariance matrix, ARH(1) covariance structure will be used.

Responder analyses

The percentage of patients who are responders based on WOMAC pain and physical function subscale scores and Patient Global Assessment scale scores defined by at least a 30% reduction and at least a 50% reduction from baseline to each post-baseline week will be summarized and plotted by the treatment group. The percentage of patients who are responders based on the Osteoarthritis Research Society International Standing Committee for Clinical Trials Response Criteria Initiative and The Outcome Measure in Rheumatology (OMERACT-OARSI) responder criteria ([Appendix 11.3](#)) will be summarized and plotted by the treatment group. Cochran-Mantel-Haenszel (CMH) test, stratified by the randomization strata will be applied for the responder analysis. Missing data is considered as non-response in this analysis.

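### As listed, the SAP's tipping-point model has no visit or treatment-by-visit term, so if coded that way it does not stress the week 16 conclusion

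*SAP*

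**What the plan says.** SAP 5.2.7.1.2 (Tipping Point Analysis) states: "Each imputed data set will be analyzed using the MMRM model with treatment, randomization strata, and relevant baseline included in the model". It gives no visit term, covariance structure or degrees-of-freedom method, and does not say at which visit the treatment comparison is made.

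The primary model in SAP 5.2.7.1.1 has the baseline score plus "treatment, randomization strata, visit, and treatment by visit interaction", fitted "with an unstructured covariance matrix to model the within-patient errors" and with Kenward-Roger degrees of freedom. Its reported result is the week 16 comparison with the control arm ("The least squares mean estimates for the mean change from baseline to week 16, as well as the difference of the estimates between fasinumab and"). The walking-pain MMRM in SAP 5.2.7.3 also lists its time terms: "treatment, week treatment-by-week interaction as fixed effects, and baseline NRS value as a covariate".

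Delta is a percentage "of the treatment effect at each corresponding visit". In SAP 5.2.7.1.2 it "will be added to the imputed values" for missing data due to adverse events or lack of efficacy. Protocol 9.5.2.1 describes the shift the other way round: a fasinumab patient's "imputed data will subtract k" times the treatment effect. The protocol gives no tipping-point model, but sets the aim as finding the k that overturns the conclusion of the primary analysis.

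**The concern.** The conclusion to be stressed is a week 16 conclusion. A repeated-measures model with one treatment coefficient and no time terms does not estimate the week 16 difference. It estimates a single effect pooled over weeks 1, 2, 4, 8, 12 and 16.

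Two consequences follow if it is run that way. The pooled estimate has a smaller standard error. The delta shift is also diluted, because early visits are mostly observed and so are not shifted. The delta reported as overturning the result may then have little to do with the delta that overturns the week 16 result. This is the planned check, on both co-primary endpoints, of how far departures from missing at random can go before the conclusion changes.

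**Working it through.** **Scale from the plan.** SAP 2.2 assumes 200 patients per arm, 15% dropout (170 evaluable), effect sizes 0.46 and 0.36, and 2-sided alpha 0.0167. In SD units the standard error is √(2/170) = 0.1085. Then 0.46/0.1085 − 2.393 = 1.85, a power of 96.8%, and 0.36/0.1085 − 2.393 = 0.93, a power of 82.3%. The stated figures of at least 96% and 82% are reproduced. After imputation all 200 per arm contribute, so the week 16 standard error is √(2/200) = 0.100 SD.

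**Standard error of the model as listed.** With an unstructured covariance, the common treatment term is the minimum-variance weighted average of the six visit-specific differences. Week 16 alone is one of the permitted weightings, so the standard error cannot exceed the week 16 value. With equal SDs at all visits and m = 6, the ratio to the week 16 standard error is:
- compound symmetry: √[(1 + 5ρ)/6], which is 0.76 at ρ = 0.5 and 0.96 at ρ = 0.9;
- AR(1): √[(1 + ρ)/(6 − 4ρ)], which is 0.61 at ρ = 0.5, 0.80 at ρ = 0.8 and 0.89 at ρ = 0.9.

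With AR(1) 0.8 and an SD that grows over time the ratio is 0.68. In the tipping runs below, week 16 carries only 0.16 to 0.36 of the weight.

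**Tipping point.** The following are assumed and not in the documents: 15% dropout in each arm, spread evenly over visits; half of it due to adverse events or lack of efficacy; the correlations; and the effect profiles. Delta is applied to fasinumab patients only, as in the protocol; the SAP sentence names no arm. Between-imputation variance is ignored in both models.

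Hand check at week 16 for a flat 0.25 SD effect: 0.15 × 0.5 = 0.075 of fasinumab patients are shifted, so 0.25 × (1 − 0.075k) = 1.96 × 0.100, which gives k = 2.88.

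The table gives large-sample results scaled to 200 per arm, with k searched up to 40 in steps of 0.25. Here k = 1 means 100% of the treatment effect. Four covariances were used: compound symmetry 0.6 and 0.8, AR(1) 0.8, and AR(1) 0.8 with growing SD.

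| True effect (SD) | Week 16, p = 0.05 | As listed, p = 0.05 | Week 16, p = 0.0167 | As listed, p = 0.0167 |
|---|---|---|---|---|
| Flat 0.46 | 6.75–7 | >40 in all four | 5.75 | >40 in all four |
| Flat 0.25 | 2.75–3 | 15, >40, 11, >40 | 0.5–0.75 | 6, 3.75, 6.25, >40 |
| Waning to 0.25 | 2.75 | >40, >40, 17.75, >40 | 0.5 | >40, >40, 11, >40 |
| Building up to 0.46 | 6.75–7 | 8.25, 6.5, 7, 7 | 5.5–5.75 | 5.75, 4.25, 5, 4.25 |

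**The term is not a week 16 test.** In 1,500 simulated trials per scenario, with an effect of 0.46 SD through week 12 and none at week 16, the model as listed rejects in 94% to 99.7% and the week 16 test in about 5%. With a delayed effect reaching 0.46 SD, the model as listed has 72% to 86% power against about 99%.

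**Sign of the shift.** WOMAC benefit is a negative change. Take an illustrative imputed change of −2.5, a treatment effect of −1.0 and 100%. The protocol gives −2.5 − (−1.0) = −1.5, a worsening. The SAP, if delta keeps the sign of the effect, gives −2.5 + (−1.0) = −3.5, an improvement.

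**The case against.** The strongest answer is that the sentence speaks of the MMRM model, and the only MMRM defined earlier for these endpoints is the primary one. The section opens by saying that it assesses robustness of the primary results, which are week 16 results. The per-protocol analysis next to it is specified just as briefly, with no terms at all. The list could also be a remnant of a week 16 ANCOVA. On either reading the test is at week 16 and the harm disappears. It is also somewhat selective to borrow the unstructured covariance from SAP 5.2.7.1.1 in the calculation but not the visit terms.

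This stands as a limit on certainty. It does not settle the text. The tipping-point sentence gives its own shorter list, where SAP 5.2.7.1.2 (treatment policy) and SAP 5.2.7.2 cross-refer when the same method is meant, and both other MMRMs with listed terms name their time terms.

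A reader might infer that the analysis is bound to make a fragile result look robust. The documents do not support that. Protocol 1.3.2 reports the slowest onset at the lowest dose of an earlier intravenous study, so a gradual effect is plausible for the 1 mg arms, and there the tipping point is similar or can come earlier. The scenario with no week 16 effect shows what the term measures, but the primary test would then normally fail and leave no positive conclusion to stress.

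A reader might also infer from the added delta that no tipping point could ever be reached. SAP 5.2.7.1.2 expects increasing delta to push the p-value above its thresholds, which works only if delta worsens the score. Adding and subtracting is therefore a wording conflict between the documents, not a faulty procedure.

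**Conclusion.** The point holds in conditional form. As listed, the tipping-point model omits visit and treatment-by-visit. If coded so over six visits, it tests a covariance-weighted average and not the week 16 difference. The standard error is then about 0.61 to 0.96 of the week 16 value. For a flat 0.25 SD effect, k at p = 0.05 is 11 or more instead of about 3; for an effect that builds up it is 6.5 to 8.25 against 6.75 to 7. These sizes rest on the assumed correlations, dropout and effect profiles and on an unstructured covariance.

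The direction of the error is not fixed, and there is none if the primary model was meant. The primary test and type I error control are unaffected. The primary analysis already recentres dropouts for adverse events or lack of efficacy at baseline, and a treatment-policy analysis is also planned, so this is not the only protection against informative dropout. It should still be corrected, because two competent programmers could follow the sentence and report tipping points that differ several-fold.

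**What to change.** In SAP 5.2.7.1.2, replace the model sentence with a statement that each imputed data set is analysed with the same MMRM as in Section 5.2.7.1.1 (baseline, treatment, randomization strata, visit, treatment-by-visit, unstructured covariance, Kenward-Roger), and that the tipping point is based on the p-value for the week 16 contrast.

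As a secondary wording point, state that delta is a positive worsening of the WOMAC change score, equal to the percentage times the absolute treatment effect at that visit. This aligns the SAP with Protocol 9.5.2.1.

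The cost is two sentences, with no new data and no change to the primary analysis. The reported tipping delta may be less favourable than the model as listed would give. If the primary model was intended all along, nothing changes but the text.

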5.2.7.2. Analysis of Key Secondary Efficacy Variable(s)

Analyses of continuous variables in key secondary endpoints will use the same analysis method as the primary efficacy variables.

Analysis of categorical variables in key secondary endpoints, the Cochran-Mantel-Haenszel approach stratified by the randomization strata will be used with missing data considered as non-response.

Control for multiplicity for both the primary and key secondary efficacy analyses are described in Section 5.2.7.1.

5.2.7.3. Analysis of Additional Secondary Efficacy Variable(s)

Analyses of continuous variables in other secondary endpoints will use the same analysis method as the primary efficacy variables.

No control for multiplicity will be made for these analyses. Tests for comparing each fasinumab dose versus placebo will utilize a nominal 2-sided alpha level of 0.05.

NRS

For the analysis of average weekly walking index joint pain using the NRS pain scale, baseline is defined as the average of the non-missing values during 7 days prior to taking study drug. For each week, the average of the non-missing values during the 7 days on or prior to that week will be used. If all values are missing for the 7 days, the value for that week is set to missing.

The MMRM model will be used for the analysis with terms for the randomization strata (K-L category [2-3 vs. 4] and index joint [hip or knee], geographic region), treatment, week treatment-by-week interaction as fixed effects, and baseline NRS value as a covariate. The least-squares (LS) means for the mean change from baseline to each week as well as the LS mean differences between fasinumab doses and placebo, with their corresponding standard errors (SEs), p-values and associated 95% confidence intervals, will be provided from the MMRM. If the model does not converge using unstructured covariance matrix, ARH(1) covariance structure will be used.

Responder analyses

The percentage of patients who are responders based on WOMAC pain and physical function subscale scores and Patient Global Assessment scale scores defined by at least a 30% reduction and at least a 50% reduction from baseline to each post-baseline week will be summarized and plotted by the treatment group. The percentage of patients who are responders based on the Osteoarthritis Research Society International Standing Committee for Clinical Trials Response Criteria Initiative and The Outcome Measure in Rheumatology (OMERACT-OARSI) responder criteria ([Appendix 11.3](#)) will be summarized and plotted by the treatment group. Cochran-Mantel-Haenszel (CMH) test, stratified by the randomization strata will be applied for the responder analysis. Missing data is considered as non-response in this analysis.

Cumulative distribution of percent change from baseline in WOMAC pain and physical function subscale scores and Patient Global Assessment scale scores will be presented by treatment group. The cumulative distribution plot displays a continuous plot of the percent change from baseline on the X-axis and the percent of patients experiencing that change on the Y-axis. Different responder definitions can be identified along the cumulative distribution curve.

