#### **6.3.2.2. Patient Global Assessment of Osteoarthritis**

The Patient Global Assessment of OA is a patient-rated assessment of patient current disease state on a 5-point Likert scale (1 = very well; 2 = well; 3 = fair; 4 = poor; and 5 = very poor). Sub-study patients will complete the assessment scale at the time points indicated in Section 6.1.

A copy of the assessment is provided in the study reference manual.

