6.1. Definition of Baseline for Variables

Unless otherwise specified, the baseline assessment for all measurements will be the latest available valid measurement prior to randomization.

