11.3. OMERACT-OARSI set of responder criteria

Note that the criteria in the diagram above are based on standardized score between 0 and 100. For this study, WOMAC pain and physical function score are between 0 and 10, so the absolute change required for response is the required change in the diagram above divided by 10; PGA is 1, 2, 3, 4 or 5, so the absolute change required for response is at least 1 point.

Signature Page for VV-RIM-00075335 v1.0

ESig Approval	 000
---------------	---

ESig Approval	 -2019 09:48:05 GMT+0000
---------------	---

ESig Approval	 19 17:12:43 GMT+0000
---------------	--

ESig Approval	 000
---------------	---

Signature Page for VV-RIM-00075335 v1.0 Approved

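### The 30% and 50% reduction rules, and the percent-change plot, do not suit a Patient Global Assessment scored 1 to 5: which patients count as responders depends on the arbitrary origin of the scale

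*SAP*

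**What the plan says.** SAP 5.2.7.3, under Responder analyses, covers WOMAC pain, WOMAC physical function and PGA, and defines response on each by "at least a 30% reduction and at least a 50% reduction from baseline to each post-baseline week". The percentages are summarised and plotted by arm, with a Cochran-Mantel-Haenszel (CMH) test stratified by the randomisation strata. On incomplete data it states: "Missing data is considered as non-response in this analysis". The section then plots the cumulative distribution of percent change for the same three scores, so that other responder cut-offs can be read from the curve.

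The scale is defined in Protocol 6.3.2.2: "The Patient Global Assessment of OA is a patient-rated assessment of patient current disease state on a 5-point Likert scale", running from 1 for very well to 5 for very poor. SAP Appendix 11.3, on the OMERACT-OARSI criteria, confirms the possible values and uses an absolute change: "PGA is 1, 2, 3, 4 or 5, so the absolute change required for response is at least 1 point". The same appendix gives the WOMAC pain and function scores a range of 0 to 10. No rescaling of PGA is specified for the percent rules.

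SAP 5.2.7.3 states that its analyses carry no multiplicity control and are tested at a nominal two-sided 0.05. The key secondary PGA endpoint, in SAP 4.4.2, is change from baseline to week 16.

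**The concern.** A percent reduction has a fixed meaning only if the scale has a true zero. On PGA the best possible state is scored 1, so the denominator includes an arbitrary unit. With five whole-number scores, the percent cuts also translate into point cuts that change unevenly with baseline. The output would be presented as two levels of response comparable with the WOMAC rates. In fact the size of improvement behind each label differs from patient to patient, and sometimes runs in the wrong order. At stake is how the PGA responder rates and the PGA cumulative plot are interpreted.

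**Working it through.** **The plan's own PGA figure.** The only computed figure for PGA is the power for mean change (SAP 2.2): 200 per arm, 15% dropout, effect size 0.36, two-sided 0.0167, at least 82% power. With 200 × 0.85 = 170 per arm, power ≈ Φ(0.36 × √(170/2) − z), where z ≈ 2.39, which gives 82.3%; the noncentral t gives 81.9%. The figure is reproduced, but it concerns mean change. The documents give no response rate or power for the PGA responder rules.

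**Inputs for the check.**
- PGA scores are whole numbers from 1 to 5, lower being better (Protocol 6.3.2.2, SAP 11.3).
- Baseline is one measurement, hence a whole number: "the baseline assessment for all measurements will be the latest available valid measurement prior to randomization" (SAP 6.1).
- Missing scores count as non-response, so no fractional imputed scores enter.
- Entry requires a WOMAC pain score of at least 4 (Protocol 4.2.1) but sets no PGA limit, so no PGA baseline is excluded by design.

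**Rule.** For baseline b, find the smallest whole drop d, with b − d at least 1, such that d/b ≥ 0.30 or d/b ≥ 0.50. The last column repeats the check with the same answers coded 0 to 4, so that the denominator is b − 1.

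| Baseline (1–5 coding) | 30% rule | 50% rule | 30% / 50% if coded 0–4 |
|---|---|---|---|
| 5 | 2 (2/5 = 40%) | 3 (3/5 = 60%) | 2 / 2 |
| 4 | 2 (2/4 = 50%) | 2 (2/4 = 50%) | 1 / 2 |
| 3 | 1 (1/3 = 33.3%) | 2 (2/3 = 66.7%) | 1 / 1 |
| 2 | 1 (1/2 = 50%) | 1 (1/2 = 50%) | 1 / 1 |
| 1 | none possible | none possible | none possible |

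**What follows.**
1. The two cuts are the same at baselines 2 and 4. The overall gap between the 30% and 50% response rates is therefore exactly the share of patients who go from 3 to 2 plus the share who go from 5 to 3.
2. Under the 30% rule a patient at 4 needs 2 points and a patient at 3 needs 1, a ratio of 2. Under the 50% rule both need 2 points, a ratio of 1.
3. A 1-point move from 2 to 1 is 1/2 = 50% and meets the stricter rule. A 2-point move from 5 to 3 is 2/5 = 40% and does not.
4. Recoding the same answers 0 to 4 moves the coincidence to original scores 2, 3 and 5, and changes who responds. A move from 4 to 3 is 1/4 = 25% as coded, not a response, but 1/3 = 33.3% after recoding, a 30% response.
5. On the cumulative plot a single point of improvement appears as 1/5 = 20%, 1/4 = 25%, 1/3 = 33.3% or 1/2 = 50%, depending on baseline. Only a few distinct values can occur.
6. A 1-point drop from 4 or 5 meets the absolute PGA change in Appendix 11.3 but fails the 30% rule in 5.2.7.3.

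**The case against.** Any relative rule asks for different absolute changes at different baselines, and the WOMAC rule does so too. That stands as a general remark. But WOMAC is scored from a true zero on 0 to 10, and patients enter with WOMAC pain of at least 4, so neither the arbitrary origin nor the unreachable response arises there for pain.

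The analysis is also peripheral. SAP 4.4.3 names only the walking-pain NRS as an additional secondary endpoint, and the key secondary responder endpoint uses WOMAC pain. This stands and limits the weight of the point.

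A reader might infer four stronger things that the documents do not support:
- **The 30% and 50% curves are one and the same.** They coincide at baselines 2 and 4 but differ at 3 and 5.
- **A patient at 4 always needs twice the improvement of a patient at 3.** This is true of the 30% rule only.
- **The CMH comparison is biased or invalid.** The rule is the same in every arm, and randomisation balances baseline PGA on average. The CMH strata (K-L score, region, index joint) do not include baseline PGA, so the response percentages still depend on the baseline mix, but that is a matter of interpretation.
- **Appendix 11.3 shows that the SAP prefers points to percentages for PGA.** It states the absolute component of a composite criterion. The criteria diagram was not available for this check, so whether a relative condition accompanies it is left open. It supports a 1-point cut and says nothing about 2 points.

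**Conclusion.** The point holds as a minor matter of interpretability. The percent rules applied to PGA give cuts that depend on the scale's origin, coincide at two of the four baselines from which response is possible, and can rank a smaller improvement above a larger one.

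The effect on any reported rate cannot be sized, because the documents give no baseline PGA distribution. The share of patients for whom the two rules are identical could in principle lie anywhere from none to all. The conclusion assumes whole-number scores and no unstated rescaling of PGA; both follow from the text. The co-primary tests, the key secondary tests, the stated power and the safety analyses are untouched.

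**What to change.** In SAP 5.2.7.3, for PGA only:
- Replace the percent rules with improvement from baseline of at least 1 point and at least 2 points. The first matches the absolute PGA change in Appendix 11.3; the second is a proposal of this review.
- Plot the cumulative distribution of point change in place of percent change.
- Show the baseline PGA distribution by arm. PGA is not among the baseline variables listed in SAP 4.1.

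Keep the percent rules and plots for WOMAC pain and function. Under the point rules the drops needed are 1 and 2 at baselines 3, 4 and 5, and the gap between the two rates is the share of patients who improve by exactly one point.

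The cost is a short text edit with no new data, best made before the first-step database lock. There are real drawbacks. PGA response would no longer be on the same percent scale as WOMAC. A patient at baseline 1 still cannot respond. A patient at baseline 2, who can meet the present 50% rule by reaching 1, cannot meet the 2-point rule. A 1-point rule also treats 5 to 4 the same as 2 to 1. The baseline table lets the reader see how many patients the floor affects.
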